### 3.3.7 Urticaria Control Test (UCT)

Urticaria disease control will be assessed by the Urticaria Control Test (UCT) using the ePRO device. The UCT is the first valid and reliable tool to assess disease control in participants with chronic urticaria. It has a retrospective approach using a recall period of 4 weeks and responses on 5-point Likert scales. The UCT questions, responses and scoring are shown in Table 4.

**Table 4 UCT questions and the scores**

1. How much have you suffered from the physical symptoms of the urticaria (itch, hives (welts) and/or swelling) in the last four weeks?				
0 = very much	1 = much	2 = somewhat	3 = a little	4 = not at all
2. How much was your quality of life affected by the urticaria in the last 4 weeks?				
0 = very much	1 = much	2 = somewhat	3 = a little	4 = not at all
3. How often was the treatment for your urticaria in the last 4 weeks not enough to control your urticaria symptoms?				
0 = very often	1 = often	2 = sometimes	3 = seldom	4 = not at all
4. Overall, how well have you had your urticaria under control in the last 4 weeks?				
0 = not at all	1 = a little	2 = somewhat	3 = well	4 = very well

A score between 0 and 4 is assigned to every answer option. Subsequently, the scores for all 4 questions are summed up. Accordingly, the minimum and maximum UCT scores are 0 and 16, with 16 points indicating complete disease control. The UCT score will be calculated when all four questions are answered, otherwise the UCT will be missing. A UCT score of <12 shows poorly controlled urticaria, a UCT score of  $\geq 12$  presents well controlled urticaria.

UCT is assessed at site at Visits 1 and 2 and at home every  $28 \pm 3$  days after Visit 2.

Change from baseline in UCT at Weeks 12 and 24 will be analysed.

Change from baseline in UCT at Weeks 52 will be analysed after the extension period.

### 3.3.8 Chronic Urticaria Quality of Life Questionnaire (CU-Q2oL)

The Chronic Urticaria Quality of Life Questionnaire (CU-Q2oL) is a 23-item assessment of CSU-specific health-related quality of life (Baiardini et al 2005). Participants are asked to rate their CSU symptoms and the impact of their symptoms over the last two weeks on several domains: Pruritus, Swelling, Impact on Life Activities, Sleep Problems, Limits, and Looks. Both the overall score and domain scores will be calculated.

The questions are scored as 1 = not at all, 2 = a little, 3 = moderately, 4 = very much, 5 = extremely. Item and scale scores are such that higher scores indicate worse QoL. To give meaningful scores, the overall and domain scores will be transformed into percentages of maximum possible score. For pruritus and swelling, if one question is unanswered, the domain will be missing. For other domains and overall score, if two or more questions are unanswered, the percentage score is not calculated. The minimum possible score is defined as 0 and the maximum possible score is defined as 100. The domain scores are shown in Table 5.

**Table 5 CU-Q2oL domains**

Domain	Item	Question
Pruritus	Pruritus / Itching	Q1
	Wheals / Hives	Q2
Swelling	Eyes swelling	Q3
	Lip swelling	Q4
Impact on life activities	Urticaria interferes with my work	Q5
	Urticaria interferes with my physical activities	Q6
	Urticaria interferes with my sleep	Q7
	Urticaria interferes with my spare time	Q8
	Urticaria interferes with my social relationship	Q9
	Urticaria interferes with my eating behavior	Q10
Sleep problems	Do you have difficulties in falling asleep?	Q11
	Do you wake up during the night?	Q12
	Do you feel tired during the day because of your bad night sleep?	Q13
	Do you have difficulties in keeping concentration?	Q14
	Do you feel nervous?	Q15
Limits	Do you feel in a bad mood?	Q16
	Do you have to put some limit in choosing your food?	Q17
	Does urticaria limits your sport activities?	Q22
Looks	Are you troubled by drugs' side effects?	Q23
	Are you embarrassed due to urticaria symptoms?	Q18
	Are you embarrassed in going to public places?	Q19

	Do you have any problems in using cosmetics?	Q20
	Do you have any limits in choosing clothes material?	Q21

The CU-Q2oL is assessed at site at Visits 1 and 2 and at home every  $28 \pm 3$  days after Visit 2. Changes from baseline in CU-Q2oL at Weeks 12 and 24 will be analysed.

Changes from baseline in CU-Q2oL at Week 52 will be analysed after the extension period.

### 3.3.9 Dermatology Life Quality Index (DLQI)

The Dermatology Life Quality Index (DLQI) is a 10-item assessment of dermatology-specific health-related quality of life ([Finlay and Khan 1994](#)). Participants are asked to rate their symptoms and the impact of their symptoms over the last week on several domains: Symptoms and Feelings, Daily Activities, Leisure, Work and School, Personal Relationships, and Treatment. Both the overall score and domain scores will be calculated.

Each question /except question 7) is scored on a four-point Likert scale: Very much = 3, A lot = 2, A little = 1, Not at all = 0, Not relevant = 0. Scoring question 7, the first part asks: 'Over the last week, has your skin prevented you from working or studying?' Scoring is for response of Not relevant = 0, and Yes = 3 (as 'prevention' is the biggest possible impact it is scored the maximum of 3). If response is No, a further question is asked: 'How much has your skin been a problem at work or studying', and scored as: A lot = 2, A little = 1, Not at all = 0.

The DLQI is calculated by summing the score of each question resulting in a maximum of 30 and a minimum of 0. The higher the score, the more quality of life is impaired.

The effects of life scores are calculated as follows:

- 0-1 = no effect at all on patient's life
- 2-5 = small effect on patient's life
- 6-10 = moderate effect on patient's life
- 11-20 = very large effect on patient's life
- 21-30 = extremely large effect on patient's life

The domain subscales are derived as shown in Table 6.

**Table 6 Subscales for DLQI**

Section	Questions	Score
Symptoms and feelings	Questions 1 and 2	Maximum 6
Daily activities	Questions 3 and 4	Maximum 6
Leisure	Questions 5 and 6	Maximum 6

Work and school	Question 7	Maximum 3
Personal relationships	Questions 8 and 9	Maximum 6
Treatment	Question 10	Maximum 3

The domain subscales for each section ([Table 6](#)) will be presented as a percentage of the maximum score (either 6 or 3). The ePRO does not allow for questions to be unanswered, no consideration is required for missing data.

The DLQI is assessed at site at Visits 1 and 2 and at home every  $28 \pm 3$  days after Visit 2. Changes from baseline in DLQI at Weeks 12 and 24 will be analysed.

Changes from baseline in DLQI at Week 52 will be analysed after the extension period.

### **3.3.10 Serum benralizumab concentration**

All PK samples will be collected before administration of study medication according in accordance with the visit schedule provided in Tables 1 and 2 of the CSP.

Concentration results below the lower limit of quantification (BLQ) will be set to LLOQ/2 for analysis and will be listed as <LLOQ.

Drug concentration information that would unblind the study will not be reported to investigative sites or blinded personnel until the study has been unblinded.

### **3.3.11 Anti-drug antibodies (ADA)**

Samples for anti-drug antibodies (ADA) will be collected before administration of study medication according (CSP Table 2). ADA variables, such as ADA responses, will be generated and analysed as per the details in [Appendix 8.2](#).

Drug concentration information that would unblind the study will not be reported to investigative sites or blinded personnel until the study has been unblinded.

## **3.4 Safety outcome variables**

Safety and tolerability will be evaluated in terms of: reported adverse events (AEs) (including serious adverse events (SAEs)), vital signs and clinical laboratory assessments.

All safety measurements will use all available data for analyses, including data from unscheduled visits and repeated measurements.

Change from baseline to each post-treatment time point where scheduled assessments were made will be calculated for relevant measurements. Safety data will be summarised by means of descriptive statistics and qualitative summaries.

No safety data will be imputed. The handling of partial/missing dates for AEs and prior/concomitant medications is detailed in [Appendix 8.3](#). Duration of AEs and prior/concomitant medications will not be calculated using imputed dates and will instead be set to missing.

### **3.4.1 Adverse Events**

AEs (including SAEs) experienced by the participants will be collected throughout the entire study and will be coded using the latest version of the Medical Dictionary for Regulatory Activities (MedDRA) that will have been released for execution at AstraZeneca/designee per the Data Management Plan.

The following events are considered treatment emergent:

- AEs with an onset date on or after the first dose of IP
- Worsening of pre-existing events on or after first dose of IP

Treatment emergent AE data will be categorized according to their onset date into the following study periods:

- AEs in the pre-treatment period are defined as those with an onset prior to the day of first dose of study treatment.
- AEs in the on-treatment period are defined as those with onset date between day of first dose of study treatment and the day of the scheduled EOT visit or date of last dose + 30 days, whichever is earlier. If the upper limit is after the end of on-study period, then the upper limit is set to the end of on-study period.
- AEs in the on-study period are defined as those with onset on or after the day of first dose of study treatment.
- AEs in the post-treatment period are defined as those with onset date after the on-treatment period defined above.

If an AE has a missing onset date then unless the stop date of the AE indicates otherwise, this will be considered an on-treatment AE. Similarly, if an AE has a partial onset date, then unless the partial onset date or the stop date indicates otherwise, this will be considered an on-treatment AE.

On-treatment AEs in the double-blind period are defined as those with an onset date between the day of first dose of double-blind period treatment and day prior to first dose in extension period, or last dose in double blind period + 30 days for those who do not enter the extension period. On-treatment AEs in the extension period are defined as those with an onset date on or after day of first dose in extension period up to day of EOT visit or last dose + 30 days.

AEs that have missing causality (after data querying) will be assumed to be related to study drug.

### 3.4.2 Clinical laboratory variables

Blood and urine samples for determination of clinical chemistry, haematology and urinalysis parameters will be taken at the times detailed in the CSP and will be assessed in a central laboratory. The parameters outlined in Section 8.2.1, Table 7 of the CSP will be collected.

In summaries, figures, and listings, lab results and normal ranges will be presented in System International (SI) units. Eosinophil data will be presented in both SI and conventional units (cells/ $\mu$ L) in summaries.

Changes in haematology and clinical chemistry variables between baseline and each post-baseline assessment will be calculated. For values recorded with a leading greater than or less than ('>', '<') symbol, the reported numeric value will be used for analysis and the value with the symbol will be included in the listings, unless otherwise specified. For example, a value of <0.01 will be analysed as 0.01 and listed as <0.01.

Absolute values will be compared to the relevant reference range and classified as low (below range), normal (within range or on limits) or high (above range). The central reference ranges will be used for laboratory variables. All absolute values falling outside the reference ranges will be flagged.

Maximum or minimum value post-baseline will be calculated over the entire post-baseline period, including the post-treatment period.

For the liver function tests: aspartate Aminotransferase (AST), alanine Aminotransferase (ALT), alkaline phosphatase (ALP), gamma-GT (GGT) and total bilirubin (TBL), the multiple of the central laboratory upper limit of the normal (ULN) range will be calculated for each data point.

$$\text{Multiple} = \text{Value} / \text{ULN}$$

That is, if the ALT value was 72 IU/L (ULN=36) then the multiple would be 2.

Participants who meet any of the following criteria at any point during the study will be flagged:

- $\text{AST} \geq 3 \times \text{ULN}$
- $\text{ALT} \geq 3 \times \text{ULN}$
- $\text{TBL} \geq 2 \times \text{ULN}$

Urinalysis data with qualitative results will be categorized as negative (0), positive (+), or strongly positive (++, +++, or >++) at each timepoint.

### 3.4.3 Vital signs and physical examination

Pre-dose vital signs (pulse, systolic blood pressure, diastolic blood pressure, respiration rate, body temperature, body weight, and height) will be obtained in accordance with the schedule provided in the CSP Table 2. Body temperature will be measured in Celsius in accordance with local standards; weight will be recorded in kilograms.

Body mass index (BMI) will be calculated from the height and weight as follows:

$$BMI \ (kg/m^2) = Weight \ (kg) / (Height \ (m))^2$$

Changes in vital signs variables between baseline and each subsequent scheduled assessment will be calculated.

Absolute values will be compared to the reference ranges in Table 7 and classified as low (below range), normal (within range or on limits) or high (above range). All values (absolute and change) falling outside the reference ranges will be flagged.

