Laboratory data for haematology and clinical chemistry will be summarised. The frequency of changes with respect to normal ranges between baseline and each post-treatment time point will be tabulated. Frequencies of clinically noteworthy values (defined in the SAP) occurring during the clinical study will also be given. Shifts from normal to abnormal between baseline and each post-baseline time point will be evaluated for urinalysis.

Vital Signs and Physical Examination

Vital sign parameters will be presented for each treatment group. Summary statistics for continuous variables cover n, mean, SD, Minimum, Q1, median, Q3, and Maximum. Frequency tables cover number and percentage of participants in the respective category.

For each scheduled post-baseline visit, descriptive statistics for all vital sign parameters will be presented for observed values and absolute change from baseline.

Changes in vital signs will be examined at each visit. Frequencies of clinically noteworthy values (defined in the SAP) occurring during the clinical study will be presented.

Details of vital sign analyses will be provided in the SAP.

Shifts from normal to abnormal between baseline and post-baseline visits will be evaluated for the physical examination.

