**Table 7 Vital signs reference ranges**

Parameter	Standard Unit	Lower Limit	Upper Limit
Diastolic Blood Pressure	mmHg	60	120
Systolic Blood Pressure	mmHg	100	160
Pulse Rate	Beats/min	40	120
Respiratory Rate	Breaths/Min	8	28
Body Temperature	Celsius	36.5	38
Weight	kg	35	200

Physical examinations (complete or brief), including height (only at baseline) and weight, will be conducted in accordance with the schedule provided in CSP Table 2. Any new findings or aggravated existing abnormalities, judged as clinically significant by the Investigator, will be reported as an AE as described in CSP Section 8.3.5.

The complete physical examination will include an assessment of the following: general appearance, skin, head and neck (including eyes, ears, nose, mouth, and throat), lymph nodes, abdomen, musculoskeletal (including spine and extremities), cardiovascular, respiratory, and neurological systems.

The brief physical examination will include an assessment of the general appearance, abdomen, cardiovascular, and respiratory system. For the brief physical examination, only information on whether the assessment was performed or not is to be recorded.

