#### **4.2.8.3 Vital Signs and Physical Examination**

For vital signs data, descriptive statistics for absolute value, change from baseline and percent change from baseline will be presented for each treatment group by scheduled visit. Summary statistics for continuous variables will present n, mean, SD, Minimum, Q1, median, Q3, and Maximum.

For physical examination data, shift tables from normal to abnormal between baseline and post-baseline visits will be evaluated.

All vital sign and physical examination data will be listed.

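### SAP 3.4.3 flags vital-sign changes against absolute-scale limits, so nearly every change is flagged, and the SAP neither defines nor tabulates the noteworthy values that Protocol 9.4.3 promises

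*SAP*

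**What the plan says.** SAP 3.4.3 first sets up a classification of the measurements themselves: each is called low, normal or high according to where it lies relative to Table 7. The next sentence widens the scope: "All values (absolute and change) falling outside the reference ranges will be flagged". The ranges are in SAP Table 7, titled "Vital signs reference ranges", whose columns are "Parameter Standard Unit Lower Limit Upper Limit". Two of its rows read "Diastolic Blood Pressure mmHg 60 120" and "Systolic Blood Pressure mmHg 100 160". There is one pair of limits per parameter and no pair for change.

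Protocol 9.4.3, under vital signs and physical examination, says: "Frequencies of clinically noteworthy values (defined in the SAP) occurring during the clinical study will be presented". It also describes frequency tables giving the number and percentage of participants per category.

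For vital signs, SAP 4.2.8.3 says that "descriptive statistics for absolute value, change from baseline and percent change from baseline will be presented for each treatment group" at each scheduled visit. The statistics are n, mean, SD, minimum, quartiles, median and maximum, and the data are also listed. SAP section 6 records two changes from the protocol: the added extension period analysis set and the wider angioedema populations. It does not mention vital signs.

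**The concern.** There are two separate problems.

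The first is a rule that cannot do its job. Changes from baseline are spread around zero, whereas the Table 7 limits sit where raw measurements sit. Applied literally, the rule marks the stable participant and leaves unmarked some of the largest rises. A programmer cannot tell whether the words about change are a slip or whether a set of change limits was left out.

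The second is a protocol commitment that the SAP does not carry through. The protocol hands the definition of a noteworthy vital sign to the SAP, the SAP does not supply it, and no corresponding table is planned. Vital signs are a named safety endpoint in both documents. At stake is a by-arm count of participants with unusual values, a standard part of a safety report.

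**Working it through.** The documents state no figure for this point, so there is nothing to reproduce. The check has three parts.

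**1. Does a change of zero pass the range check?** SAP 3.1.2 defines change as the post-baseline value minus the baseline value. A change *d* escapes the flag only if L ≤ *d* ≤ U, with L and U from Table 7.

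| Parameter | L | U | Is 0 inside? | Smallest rise that escapes |
|---|---|---|---|---|
| Diastolic BP (mmHg) | 60 | 120 | No | +60 |
| Systolic BP (mmHg) | 100 | 160 | No | +100 |
| Pulse (beats/min) | 40 | 120 | No | +40 |
| Respiratory rate (breaths/min) | 8 | 28 | No | +8 |
| Temperature (°C) | 36.5 | 38 | No | +36.5 |
| Weight (kg) | 35 | 200 | No | +35 |

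Every L is positive, so no change and every fall are flagged for all six parameters. This part needs no assumption.

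**2. What share of changes is flagged?** This needs the spread of the changes, which the documents do not give. Assume change is Normal with mean 0 and standard deviation σ. Then

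share flagged = 1 − [Φ(U/σ) − Φ(L/σ)].

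The ranges of σ below are assumptions.

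| Parameter | Assumed σ | Share flagged |
|---|---|---|
| Diastolic BP | 5 to 15 | 99.997% to 100% |
| Systolic BP | 8 to 20 | 100% |
| Pulse | 6 to 15 | 99.6% to 100% |
| Respiratory rate | 1.5 to 5 | 94.5% to 100% |
| Temperature | 0.2 to 0.8 | 100% |
| Weight | 2 to 8 | 99.999% to 100% |

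Worked case, respiratory rate at σ = 5: L/σ = 8/5 = 1.6 and U/σ = 28/5 = 5.6. With Φ(1.6) = 0.9452 and Φ(5.6) ≈ 1, the share is 1 − (1 − 0.9452) = 94.5%. At σ = 3 it is 99.6%. (Entries of 100% are rounded.)

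**3. Is the protocol's frequency table planned anywhere in the SAP?**

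- *Definition.* The SAP does not use or define the term *clinically noteworthy*. The nearest thing is the low/normal/high classification in 3.4.3.
- *Table.* SAP 4.2.8.3 gives continuous statistics and listings for vital signs. The classification in 3.4.3 feeds no table there.
- *Declaration.* SAP section 6 has no entry on it.
- *Comparison within the SAP.* Laboratory parameters get shift tables against reference ranges (4.2.8.2), and physical examination gets normal-to-abnormal shift tables (4.2.8.3). Vital signs get neither.
- *Flag wording.* The laboratory rule in SAP 3.4.2 is nearly the same sentence but is confined to absolute values.

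**The case against.** The strongest reply is that this is a stray phrase with little consequence. The authors can hardly have meant to compare changes with absolute limits. No summary or test in the SAP uses the vital-sign flag, and a competent programmer would query it. The general text might also be said to cover the missing table: SAP 4.1 has categorical data summarised by frequency and percentage, and SAP 3.4 mentions qualitative summaries of safety data. Finally, Protocol 8.3.5 has vital-sign deterioration reported as an adverse event when it is serious, leads to discontinuation of study drug or is judged clinically relevant, and adverse events are tabulated by arm.

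Much of this stands as a limit on importance. It does not remove the point. The sentence has to be programmed from, and it offers two incompatible repairs. The general statements name no vital-sign category to tabulate and do not define a noteworthy value. Adverse-event reporting depends on investigator judgement and is not the frequency table that the protocol describes.

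A reader might infer more than the documents support:

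- *That vital-sign outliers cannot be found at all.* The same sentence flags absolute values against Table 7, and that flag works.
- *That stable participants are classified as low.* The low/normal/high label is given to absolute values only; changes are merely flagged.
- *That extremes are never set side by side by arm.* The by-visit minimum and maximum show them. What is missing is the number of participants concerned.
- *That the SAP withdrew the analysis.* Nothing withdraws it; the SAP leaves it undefined and unplanned.
- *That the protocol promised a count against Table 7 within an on-treatment window.* It specifies neither: the definition is left to the SAP, and the period is the clinical study.

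**Conclusion.** Both parts hold, and both are minor. That a change of zero fails all six range checks follows from Table 7 alone. The percentages rest on assumed Normal changes centred at zero with the stated standard deviations; the lowest, 94.5%, is for respiratory rate at the widest assumed spread. The defect is confined to the change flag. On the second part, no planned table counts participants with noteworthy or out-of-range vital signs by treatment group, the term that such a table depends on is undefined, and the departure from the protocol is not declared. The effect is on safety presentation only. The primary and key secondary efficacy analyses are untouched.

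**What to change.** 1. In SAP 3.4.3, delete the reference to change so that only absolute values are flagged, matching the laboratory rule in 3.4.2. If change flags are wanted, add separate change limits to Table 7.
2. Define *clinically noteworthy* for vital signs in the SAP. The low and high categories against Table 7, already derived under 3.4.3, are one available choice; the SAP should state it as its own definition.
3. Add to SAP 4.2.8.3 a table of the number and percentage of participants with at least one such post-baseline value during the study, by parameter and treatment group.

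The cost is a few lines of SAP wording and one table. If the existing categories are used, no new derivation is needed. No extra data are collected and no efficacy output changes.
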